Universität zu Köln

STUDY PROTOCOL

AN INTERNATIONAL MULTICENTER REGISTRY STUDY ON AUTOSOMAL RECESSIVE POLYCYSTIC KIDNEY DISEASES (ARPKD) - AREGPKD

Principal Coordinating Investigator:

[name] [name] Department of Pediatrics Cologne University Hospital [name] 50937 Cologne Germany

Version of 01 March 2013, Version v2-01

The information in this registry study protocol is strictly confidential. It is for the use of the investigators, registry study personnel, ethics committee, the authorities, and study subjects only. This registry study protocol may not be passed on to third parties without the express agreement of the sponsor or the Principal Coordinating Investigator (PCI)

I. Signatures

All persons who made a significant contribution to the preparation of the study protocol (protocol development committee) should sign this page.

[name] (Principal Coordinating Investigator, PCI) On behalf of University of Cologne	Signature	01.03.2013 Date
[name] (Deputy of the PCI) On behalf of University of Cologne	Signature	01.03.2013 Date
[name] (Head of Pediatric Study Center) On behalf of University of Cologne	Signature	01.03.2013 Date
[name] (Chair of Pediatrics) On behalf of University of Cologne	Signature	01.03.2013 Date
[name] (Statistician) Department of Medical Biometry, Heidelberg Universi	Signature ity Hospital	01.03.2013 Date

II. Synopsis

Principal Coordinating Investigator:	University of Cologne [name] 50923 Cologne Germany
	Represented by:
	[name] [name] Department of Pediatrics Cologne University Hospital [name] 50937 Cologne
	Germany
Title of the clinical study:	An International Multicenter Registry Study on Autosomal Recessive Polycystic Kidney Diseases (ARPKD) - ARegPKD
Type of study, study design, methodology:	Non-interventional, multicenter, multinational, open, non- randomized registry study
Primary study objective:	Deep Phenotyping and detailed analysis of longterm clinical courses of ARPKD patients. Associated biobanking, reference histology and Next Generation Sequencing approach to understand underlying pathophysiological mechanisms.

Page 3 of 38

(ARPKD) Key inclusion criteria: Autosomal Recessive Polycystic Kidney Disease • (ARPKD) of any age, diagnosed either o by histology o by molecular assessment o or clinically according to the criteria established by Zerres et al. (1996, Acta Paediatr. 85:437-455) informed consent of patient and/or parents resp. legal representatives Key exclusion criteria: • Genetic proof of other cystic kidney disorders (e.g. NPHP, ADPKD) Histological proof of other cystic kidney disorder • Clinical Proof of other cystic kidney disorder

Time plan: Start registry study: 1. August 2012

ARegPKD Study protocol V2.01, 01.03.2013

Medical Condition and Key Medical condition or disease to be investigated: inclusion criteria:

Autosomal Recessive Polycystic Kidney Disease •

ARegPKD Study protoco	1 v2.01, 01.03.2013	Page 5 of 38
Statistician:	[name], M. Sc.	
	Insitute of Medical Biometry and Informatics	
	University of Heidelberg	
	[name]	
	69120 Heidelberg	
	Germany	
Statistical methods:	Standard appropriate statistical approaches to a ups of patient's survival, renal function etc. In ca data appropriate methods (e.g. multiple imputat to handle them. Furthermore the aspect of mult be considered.	ase of missing ion) will be used
GCP conformance:	As far as applicable the present study will be co accordance with the valid versions of the study internationally recognised Good Clinical Practic (ICH-GCP), including archiving of essential doc	protocol and the e Guidelines

III. Table of contents Ι. 2 Signatures II. **Synopsis** 3 Table of contents III. 6 III.a) List of tables 8 III.b) List of figures 8 1. Introduction 10 2. Objectives of the registry study 11 2.1. Rationale for the registry study 11 2.2. Primary objective 11 2.3. Secondary and other objectives 12 Organisational and administrative aspects of the study 3. 13 3.1. Principal Coordinating Investigator 13 3.2. Statistics 13 3.3. Further committees 13 3.3.1. Steering Committee 13 3.4. Study laboratories and other technical services 14 3.5. Central organisation units 16 3.6. Investigators and study sites 16 4. Study conduct 18 4.1. General aspects of study design 18 4.1.1. Time plan 18 Discussion of study design 4.2. 18 4.3. Selection of study population 19

ARegPKD

ARegPKI	D Study protocol V2.01, 01.03.2013	Page 7 of 38
4.3.1	I. Inclusion criteria	19
4.3.2	2. Exclusion criteria	20
4.4.	Withdrawal of study subjects after study start	20
4.5.	Measures within ARegPKD	19
4.6.	Data quality assurance	21
4.6.1	I. Data management	23
4.6.2	2. Archiving	23
5. Eth	ical and regulatory aspects	24
5.1.	Independent ethics committee	24
5.2.	Ethical basis for the clinical study	24
5.2.1	 Legislation and guidelines used for preparation 	24
5.3.	Obtaining informed consent from study subjects	24
5.4.	Data protection	25
6. Sta	tistical methods and sample size calculation	27
6.1.	Statistical and analytical plan	27
7. Use	e of study findings and publication	27
7.1.	Publication	28
8. Am	endments to the study protocol	29
9. App	pendices	30
9.1.	Study sites and principle investigators	30
9.2.	Protocol Agreement Form	37
9.3.	Steering Committee	37
9.4.	Study laboratories and other technical resources	37

ARegPKD	Study protocol V2.01, 01.03.2013	Page 8 of 38
III.a)	List of tables	
Table 1:	Time plan of the study	18
III.b)	List of figures	
Figure 1:	ARegPKD flow sheet for the first years	1820

IV. Abbreviations

abbreviation	meaning
ARPKD	Autosomal recessive polycystic kidney disease
ADPKD	Autosomal dominant polycystic kidney disease
ARegPKD	Acronym of the ARPKD registry study consortium
ESCAPE	European Study Consortium for Chronic Kidney Disorders Affecting Pediatric Patients
GPN	Gesellschaft für Pädiatrische Nephrologie
NGS	Next Generations Sequencing
SC	Steering Committee
PCI	Principal Coordinating Investigator
PKHD1	Polycystic Kidney and Hepatic Disease 1
RCAD	Renal cysts and diabetes syndrome

1. Introduction

Polycystic kidney disease represents a major socio-economic medical problem within the EU. The adult-onset Autosomal Dominant Polycystic Kidney Disease (ADPKD) is a very frequent monogenetic diseases and a major cause of dialysis-requiring end stage renal failure. Autosomal Recessive Polycystic Kidney Disease (ARPKD) is the rare pediatric form of cystic kidneys. It has a tremendous and early impact on child health e.g. frequently requiring breathing assistance within the first year of life. Kidneys are often grossly enlarged at birth and there is mandatory hepatic involvement. ARPKD occurs with an estimated incidence of 1:20.000. Still, ARPKD is responsible for up to 50% of patients with cystic kidneys in pediatric centers. There is major unexplained phenotypic variability. ARPKD is caused by mutations in a single gene *PKHD1*, wich encodes a huge transmembrane protein called Fibrocystin. The protein localizes to primary cilia of cells, classifying ARPKD as a ciliopathy. Fibrocystin is also involved in the regulation of pathways affected in ADPKD.

2. Objectives of the registry study

2.1. Rationale for the registry study

Cystic kidney diseases are a major cause of dialysis-requiring end stage renal failure in Europe. While some insights into the underlying pathomechanisms have been obtained there is still no effective treatment for this common and severe group of disorders. ARegPKD addresses this issue by studying the most severe form of cystic kidney diseases, ARPKD. The pathophysiology, clinical heterogeneity and long-term evolution of ARPKD remain poorly understood, explaining why there is currently no causative treatment. Even in most-advanced medical centers mortality remains high at up to 30% mainly related pulmonary problems. Kidney dysfunction is progressive leading to early end stage renal failure, and a need for dialysis and kidney transplantation in ~50% of the patients within the first two decades of life. In addition liver affection is obligatory, so severe liver fibrosis and a portal hypertension develop in a major fraction of patients. Combined liver and kidney transplantation is required in case of renal and hepatic failure. Severe and very early arterial hypertension is common and treatment often remains challenging. No clinical classifications, clinical risk factors or treatment guidelines for these challenges have been established so far and experience remains sparse even in large pediatric centers.

Therefore a multicenter, multinational approach is needed to perform deep phenotyping along with genetic analysis of a well-described cohort to increase our knowledge about this severe kidney disorder. Furthermore, the international comparison of current treatment strategies is required to establish international evidence-based treatment standards.

2.2. Primary objective

ARegPKD aims to contribute to the fight against life-threatening disorders of early childhood as well as the fight against end stage renal failure.

ARegPKD will increase insight into the pathomechanisms underlying ARPKD and set up conditions for the establishment of clinical studies on ARPKD. Using a web-based database

we will collect initial and follow up clinical data of ARPKD patients. Deep phenotyping will be combined with a Next Generation Sequencing Approach to study genetic modifiers that would explain the phenotypic variations seen in ARPKD. We will also look for clinical or biochemical risk markers. An ARPKD bio-repository as well as reference histology will be set up to generate a deeply characterized cohort that may be important for the set-up of future clinical trials.

2.3. Secondary and other objectives

As a multinational European registry with involvement of EU-neighbouring countries ARegPKD can differentiate incidence, available treatment options and outcomes in the different regions of Europe and unmask inequalities in access to health care and quality of disease management in this rare disorder. At the same time the scientific exchange within the project will make state-of-the-art medical decisions in the field of pediatric cystic kidney diseases available for affected children in all included areas. ARegPKD will also be able to establish equal standards in participating countries for this life-threatening and little understood disorder.

As a consequence of our project current emerging molecular therapies for autosomal dominant polycystic kidney disease (ADPKD) can be evaluated for the rare but by far more dramatic ARPKD in an existing and deeply-characterized cohort. These clinical studies will be the first step to evidence-based treatment in a severe disorder of early childhood with the potential to fundamentally reduce mortality.

3. Organisational and administrative aspects of the study

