3.6. Investigators and study sites

This clinical study will be carried out as a multicenter open non-randomized registry study at ~90 international study sites. If necessary, further qualified study sites may be recruited to the study.

Regional coordinators will be named for groups of centers. In addition to the central study coordinators these regional coordinators can help the study sites with regulatory requirements (e.g. ethics committee) and are contact persons for potential problems of data acquisition or data entry.

A list of study sites involved, including information on the principal investigators and the corresponding regional coordinators will be kept and continuously updated. A list of the study with names of the principal investigators is given in Appendix 11.1.

Requirements for investigators and study sites

Investigators should have ample experience in the field of pediatric nephrology. As most Centers have been involved in previous either GPN- or ESCAPE-based studies these partners know the course of a web-based registry. Sites need to have access to the internet.

4. Study conduct

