4.2. Discussion of study design

ARegPKD will collect pseudonymized information from patients suffering from ARPKD. Webbased registry studies are an innovative, highly efficient and data protection-sensitive approach to collect information in rare disease conditions. Encompassing the majority of European countries and citizens, making use of dedicated, highly specialized pediatric nephrology units and embarking into innovative analytical approaches such as genome-wide sequencing combined with tissue expression studies, the ARegPKD consortium will take full advantage of the population size, the excellent organization of high-end health care and the biotechnological lead of the European Community as a whole.

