4.3. Selection of study population

As a registry for a rare disease, ARegPKD will initially mainly affect patients suffering from autosomal recessive polycystic kidney disease (ARPKD). The estimated incidence of this disease is 1:20.000. Within the ARegPKD we estimate that there are at least 300-500 pediatric patients included into the registry who will initially benefit e.g. by access to chronic health care. All male and female, pediatric and adult ARPKD patients that are currently seen in the participating centres can be included. However, as ARPKD is mainly a pediatric disorder, most of the patients will be children.

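### Section 2.3 says the registry can compare ARPKD incidence between European regions, but the design provides neither a denominator nor any measure of how completely cases are captured

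*Protocol*

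**What the plan says.** The claim is in Protocol section 2.3: "ARegPKD can differentiate incidence, available treatment options and outcomes in the different regions of Europe and unmask inequalities in access to health care". It carries no qualification, and the same sentence goes on to inequalities in access to care.

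The other relevant statements in the Protocol are:

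- **Who can enter.** Section 4.3: "pediatric and adult ARPKD patients that are currently seen in the participating centres can be included". Under section 4.1.1, patients are met at routine visits and the first data are collected retrospectively, with prospective recruitment developing later. Section 4.6.1 recruits through the participating centres of two paediatric nephrology networks.
- **Consent.** Section 5.3 allows no enrolment without consent. Section 4.4 allows data to be deleted or anonymised on request after withdrawal.
- **Sites.** Section 3.6 describes a "multicenter open non-randomized registry study at ~90 international study sites" and leaves room for more. The site list in section 9 includes centres in Brazil, Chile and Colombia. Section 4.2 describes the reach as "Encompassing the majority of European countries and citizens".
- **Size and frequency.** Section 4.3: "The estimated incidence of this disease is 1:20.000", and "we estimate that there are at least 300-500 pediatric patients included into the registry". The incidence is an input to the protocol, not something the registry has estimated.
- **Analysis.** Section 6.1 plans mainly descriptive statistics, leaves inferential analyses to a statistical analysis plan, and promises in general terms to look at bias. It names no method for incidence.

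**The concern.** An incidence rate needs all new cases in a defined period, or a known fraction of them, over a defined population at risk. For a congenital disease that population is births. The protocol sets up neither part.

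The numerator is a consenting subset of patients at participating centres. A child who dies before reaching such a centre, is followed elsewhere, is undiagnosed, or whose family declines does not appear. No log of these cases is described. Section 2.1 puts mortality at up to 30%, mainly from pulmonary problems, so losses before contact may matter, and they need not be equal across regions.

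What is at stake is a false regional finding. A region with more active centres, higher consent or better early survival would show more registered cases per birth and could be reported as having a higher incidence. Conclusions about unequal access drawn from such a difference could even run the wrong way, because better access raises the count.

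**Working it through.** **Step 1: what an incidence comparison needs, against what the protocol describes.**

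| Needed | Described in the Protocol |
|---|---|
| All new cases, or a known fraction | Consenting patients seen at participating centres (4.3, 5.3); retrospective at first (4.1.1) |
| Count of eligible cases not enrolled | None in the measures listed in 4.5 |
| Count of deaths before contact | None |
| Births or catchment population by region | None |
| Completeness check | None; 4.6.1 checks entered data, not missing cases |

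This comparison needs no outside figure, and the conclusion rests on it.

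**Step 2: size of the artefact.** For a region with B births, true incidence I and capture fraction c, the expected registered count is B × I × c. The apparent incidence is I × c. For two regions with the same I:

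apparent ratio = c2 / c1 = 0.15 / 0.10 = 1.5.

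The true incidence cancels, so the whole ratio comes from ascertainment. Could it pass for a real difference? Assume 1 million births a year in each region, 18 cohorts and 30% mortality:

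- living pool per region = 1,000,000 / 20,000 × 18 × 0.7 = 630;
- registered = 63 (10%) and 94.5 (15%);
- z = ln(1.5) / √(1/63 + 1/94.5) = 0.405 / 0.163 ≈ 2.5.

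Under these assumptions a conventional test would call the spurious difference significant. The capture fractions are hypothetical.

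**Step 3: how complete might capture be?** The 300-500 cannot be reproduced, because the protocol gives no births, catchment or capture rate behind it. What can be shown is conditional:

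living pool = births per year × (1/20,000) × 18 × (1 − mortality); capture = 300 or 500 / pool.

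Inputs from the documents are 1:20,000 and 300-500 (section 4.3) and mortality of 0-30% (section 2.1 gives up to 30%, a ceiling). **Assumptions** are annual births of 2-8 million, 18 birth cohorts, and mortality applied as one flat reduction.

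| Births/year (assumed) | New cases/year | Mortality | Living pool | 300 / pool | 500 / pool |
|---|---|---|---|---|---|
| 2 million | 100 | 30% | 1,260 | 23.8% | 39.7% |
| 2 million | 100 | 0% | 1,800 | 16.7% | 27.8% |
| 4 million | 200 | 30% | 2,520 | 11.9% | 19.8% |
| 4 million | 200 | 0% | 3,600 | 8.3% | 13.9% |
| 8 million | 400 | 30% | 5,040 | 6.0% | 9.9% |
| 8 million | 400 | 0% | 7,200 | 4.2% | 6.9% |

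The range is about 4-40%.

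**Step 4: the same relation inverted.** Births per year at which 300-500 children would be complete capture:

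- lowest: 300 × 20,000 / 18 ≈ 0.33 million;
- highest: 500 × 20,000 / (18 × 0.7) ≈ 0.79 million.

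If the covered countries have more births than that, 300-500 children is incomplete capture.

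**The case against.** The best case for the protocol has five parts.

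1. **The coverage figure is not the protocol's.** A reader might infer that 1:20,000 and 300-500 patients by themselves prove low coverage. They do not: without annual births they give no coverage at all. The 300-500 is also introduced as a minimum, and the registry is open-ended in time and in sites, so eventual capture could be higher. This stands, and the 4-40% is therefore only an illustration.
2. **Centre coverage cannot be judged here.** The site list available for this review is incomplete, so some countries may have every referral centre taking part. This stands too, and nothing here asserts that coverage is poor in any country. But full centre participation would still leave non-consenters and deaths before contact uncounted.
3. **An analysis plan could add a denominator.** National birth statistics could indeed be brought in later. The capture fraction could not, because the cases that were not enrolled are not recorded under the measures described. The general promise in section 6.1 to examine bias does not supply it.
4. **Prospective recruitment will grow.** It will, and that helps date new cases. It does not show what share of them was enrolled.
5. **It is one word in an aspirational sentence, with no incidence endpoint specified.** That limits the weight of the point. Still, section 6.1 foresees inferential analyses of the stated research questions, so the claim could be carried into testing.

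**Conclusion.** The point holds for incidence. Section 2.3 asserts a capability that the described design lacks, and later analysis cannot recover a capture fraction that was never measured. This rests on the protocol text alone.

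The size of the error in any actual comparison is unknown. The spurious ratio equals the ratio of capture fractions, for example 1.5 at 15% against 10%. Capture of about 4-40% depends on the assumed 2-8 million births a year, 18 cohorts, 0-30% mortality, and on treating a floor of 300-500 as the total.

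A reader might go further and conclude that the whole secondary objective fails. The documents do not support that. Treatment options and outcomes can be compared among enrolled patients, subject to selection, and inequalities in care can be described on that basis. Because only one component of a secondary objective is affected, this should be corrected but does not undermine the registry.

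**What to change.** **Preferred:** delete incidence from section 2.3 and state instead that the number and characteristics of registered patients will be reported by region. The cost is a rewording of one sentence and a more modest claim.

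**Alternative, if incidence is to stay:** limit it to named regions in which all referral centres take part, and:

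- count prospectively diagnosed cases only;
- use official live births for the same area and period as the denominator;
- obtain a yearly anonymous count of cases not enrolled, including refusals and deaths before contact, where local law allows;
- report the resulting capture fraction beside every regional rate.

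The cost is that yearly count, and probably only some countries could contribute.

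With either option, add a sentence saying that regional comparisons of treatment and outcome apply to enrolled patients.

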4.1.1. Time plan

Patients will be seen in their corresponding center during routine visits. After informed consent doctors will introduce the data into the web-based data base and will fill-in an initial questionnaire on clinical presentation etc. Initially this will be retrospectively done, but prospective recruitment will develop over the year. Patients will then be followed by a yearly follow-up questionnaire.

Data of some patients may have also been included in other comparable pediatric nephrology studies or trials, e.g. the 4C study (The Cardiovascular Comorbidity in Children with Chronic Kidney Disease Study). After explicit informed consent specific data points (e.g. date of birth, prenatal history, laboratory values on kidney function etc.) may be transferred from the corresponding database to the ARegPKD database. This will only affect data points that have already been obtained.

Table 1: Time plan of the registry study

Start registry study	1 August 2012

End of the clinical study

ARegPKD is a retro- and prospective registry study without a defined time limit.

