4.6. Data quality assurance

4.6.1. Data management

Well-established methods will be used to achieve the specific goals of ARegPKD. Via the participating centers of the German Pediatric Nephrology association (GPN) and the European Study Consortium for Chronic Kidney Disorders Affecting Pediatric Patients (ESCAPE Network) we recruit patients suffering from autosomal recessive polycystic kidney disase (ARPKD). After informed consent patient data will pseudonymously be entered into a web-based database. Data protection will be secured by use of SSL-connections and password restriction of the webpage.

To minimize the risks that data quality might suffer from incomplete or erroneous data entries in the web-based data base, the online forms will require mandatory inclusion of key variables, and include automated entry checks using predefined plausibility ranges. By these precautions the risk of data entry errors will be minimized. Data entries will also be reviewed by a pediatric nephrologist in random checks and during regular interims analysis. Queries will be sent to the local investigators in cases of implausibility or doubt. In case of major problems with accomplishing regular local data entries, the associated partner in charge will provide support by sending staff to educate local investigators or take over data entry tasks.

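### Section 2.3 promises to show inequalities in access to care, but a registry of patients already seen at participating specialised centres cannot show inequality in reaching those centres.

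*Protocol*

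**What the plan says.** Protocol section 2.3 makes two linked claims without qualification: that "ARegPKD can differentiate incidence, available treatment options and outcomes in the different regions of Europe", and that the registry can "unmask inequalities in access to health care and quality of disease management in this rare disorder".

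The sampling frame is set elsewhere in the protocol:

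- Section 4.3: "All male and female, pediatric and adult ARPKD patients that are currently seen in the participating centres can be included".
- Section 4.1.1: "Patients will be seen in their corresponding center during routine visits". Data are entered after consent, at first retrospectively.
- Section 4.2 describes the consortium as "making use of dedicated, highly specialized pediatric nephrology units".
- Section 3.6: "Investigators should have ample experience in the field of pediatric nephrology". It also notes that "most Centers have been involved in previous either GPN- or ESCAPE-based studies".
- Section 4.6.1 gives the recruitment route: "Via the participating centers of the German Pediatric Nephrology association (GPN) and the European Study Consortium for Chronic Kidney Disorders" (the ESCAPE network).

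On bias, section 6.1 has one general sentence saying that possible sources will be examined and taken into account. It names no particular bias. The text available mentions no regional births or catchment population, no check of completeness, and no link to birth, death or dialysis registers.

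**The concern.** Being under care at a participating centre is a condition for being in the data. A comparison of regions within that sample therefore says nothing about how many affected children in each region never got there. That is one of the main things a reader would understand by inequality in access to health care, particularly since section 4.2 presents the consortium as covering most European countries and citizens.

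The disease makes this more than a formality. Section 2.1 puts mortality at up to 30% even in the most advanced centres, mainly from pulmonary problems, and section 1 says that breathing support is often needed in the first year of life. Children who die before referral are a plausible group in whom access failed, and a frame of patients currently seen does not contain them.

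At stake is the interpretation of a secondary objective with health-policy content. Similar results across regions could be taken as reassurance about access that the data cannot give.

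**Working it through.** The protocol gives no calculation on this point, so there is no figure to reproduce. The check sets the objective against the frame and then illustrates the possible size.

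**Objective against frame**

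| Component of 2.3 | What it needs | Available from enrolled patients? |
|---|---|---|
| Reaching specialist care | Affected patients who did not reach a centre, or a regional denominator | No |
| Access to steps after referral (e.g. dialysis, transplantation) | Dates or ages among patients in care | Yes, conditional on arrival |
| Quality of management, and outcome | Course of patients in care | Partly, conditional on arrival |

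The incidence claim in the same sentence meets the same obstacle. At the protocol's 1:20,000, one expects 1,000,000 / 20,000 = 50 cases per million births, but no regional birth counts are described against which to set enrolment.

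**Size, under stated assumptions**

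Inputs:
- Survival in centres, S_c = 1 − 0.30 = 0.70, from section 2.1. Because that mortality is an upper figure, 0.70 is the lowest centre survival it implies.
- Share of region B's patients reaching a centre, f = 0.9, 0.75 or 0.5 (assumed).
- Survival outside centres, S_o = 0.2 to 0.6 (assumed).
- Region A has full access (f = 1).

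True survival in B = f × S_B + (1 − f) × S_o, where S_B is survival in B's centres. True gap = 0.70 − true survival in B. Registry gap = 0.70 − S_B.

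*Case 1: equal care inside centres, S_B = 0.70.* The registry gap is 0 by construction. The true gap reduces to (1 − f)(0.70 − S_o):

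| f | S_o = 0.2 | S_o = 0.4 | S_o = 0.6 |
|---|---|---|---|
| 0.9 | 5 points | 3 | 1 |
| 0.75 | 12.5 | 7.5 | 2.5 |
| 0.5 | 25 | 15 | 5 |

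*Case 2: worse outcomes inside B's centres, S_B = 0.55 (assumed).* The registry gap is 0.70 − 0.55 = 15 points throughout. The true gap is:

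| f | S_o = 0.2 | S_o = 0.4 | S_o = 0.6 |
|---|---|---|---|
| 0.9 | 18.5 points | 16.5 | 14.5 |
| 0.75 | 23.75 | 18.75 | 13.75 |
| 0.5 | 32.5 | 22.5 | 12.5 |

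In case 2 the registry shows a gap. It understates the true one when S_o is below S_B (0.2 and 0.4) and overstates it when S_o is above S_B (0.6). The direction is therefore not fixed; it depends on who is missed.

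A difference inside centres is also within statistical reach. Splitting the expected 300 or 500 patients into two equal regional groups, 70% against 55% survival has power of about 0.77 or 0.94 (two-sided 0.05; split and level assumed).

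**The case against.** The strongest reply is that section 2.3 speaks of access to health care, not of access to specialist centres. Its sentence also names treatment options, outcomes and quality of management, and section 2.1 names dialysis, kidney transplantation and combined liver and kidney transplantation. Regional differences in these can be seen among enrolled patients. This stands: the objective is partly answerable, and what is missing is its limit.

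Second, the zero registry gap in case 1 is an input, since equal in-centre survival is assumed. This also stands. The tables show what can stay hidden, not what will happen.

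Third, nothing in the protocol says that similar outcomes will be read as equal access; the analysis is mainly descriptive, inference is left to a statistical analysis plan, bias is to be examined, and further sites may join. This answers only part of the point. An analysis plan can add caveats, but it cannot recover patients outside the frame. Section 3.6 confines added sites to qualified ones, so the condition on entry remains.

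A reader might go further and infer that poor-access regions will necessarily look as good as the others, with bias always towards no inequality. The documents do not support that. Late arrival or fewer options inside a region's centres would make it look worse, and case 2 shows error in both directions.

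**Conclusion.** The point holds in a limited form. Section 2.3 claims without qualification a property that the design has only in part. Inequality in reaching specialist care cannot be shown, because those who fail to reach it are not enrolled and no denominator or outside source is described. Regions with poor access can look similar to regions with good access.

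Under the assumptions above, a true difference of 1 to 25 percentage points in survival could accompany a registry difference of 0 when in-centre outcomes are equal. When they are not, an observed 15 points could stand for a true 12.5 to 32.5. These ranges rest on assumed shares reaching a centre and assumed survival outside; only the 30% mortality comes from the protocol. The structural conclusion does not depend on them.

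The primary objective is not affected. The change is still worth making, because it alters what the registry may conclude on a policy question.

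**What to change.** 1. Limit section 2.3 to differences between countries in management, outcome and access to steps after referral, among patients at participating centres.
2. Base the access part on intervals from chart data, such as age at first suspicion, first visit to the centre, genetic diagnosis, start of kidney replacement and transplantation. The questionnaire is not shown, so add fields only where it lacks them.
3. State that similar outcomes among enrolled patients are not evidence of equal access to specialist care.

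If the sponsor wishes to keep the wider claim, the protocol would need regional catchment and birth denominators and an external check of completeness, which is a much larger undertaking.

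The cost of the limited version is rewording and possibly a few age or date fields. Its downside is a narrower secondary claim. The intervals also remain conditional on reaching a centre, so they describe delay among those who arrived and not failure to arrive.
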